7.2.16 Hematology

Blood samples for hematology tests will be collected at the time points as specified in the Schedule of Assessments. All laboratory tests must be reviewed and signed by the principal investigator or qualified designee. Additionally safety laboratory assessments may be performed for subject safety.

The tests listed in [Table 3](#) will be conducted and analyzed by standard laboratory procedures.

Additional procedures deemed necessary as part of standard of care or as required by local laws and regulations may be performed at the Investigator's discretion.

7.2.17 Plasma AMG 986 Concentrations

Blood samples for PK assessments will be collected at the time points as specified in the Schedule of Assessments.

7.2.18 Estimated Glomerular Filtration Rate

For determining eligibility, estimated glomerular filtration rate (eGFR) will be calculated by the estimated Modification of Diet in Renal Disease (MDRD) formula based on serum creatinine, age, sex, and race values at time points indicated in the Schedule of Assessments.

$eGFR \text{ in mL/min per } 1.73 \text{ m}^2 = 175 \times \text{SerumCr}^{-1.154} \times \text{age}^{-0.203} \times 1.212 \text{ (if patient is black)} \times 0.742 \text{ (if female)}$

7.2.19 Hepatitis B Surface Antigen and Core Antibody, Hepatitis C Antibody and HIV Status

Hepatitis B surface antigen and core antibody, Hepatitis C antibody, and human immunodeficiency virus (HIV) titers will be assessed at screening only and must be confirmed negative to be eligible for this study.

7.2.20 Concomitant Medications and Adverse Event Reporting

Subjects will be assessed for concomitant medication(s) usage during each visit. Any concomitant medication use reported throughout the study will be recorded in the source documents and the CRF.

Subjects will be assessed for adverse events/serious adverse events during each visit. Determination of the severity of all adverse event(s) will be consistent with Common Terminology Criteria for Adverse Events (CTCAE) V4 ([Appendix A](#)) unless specified otherwise. Adverse events will be captured in the source document and on the CRF when reported or observed.

7.3 Approximate Phlebotomy Volume

Subjects enrolled in this study will agree to provide whole blood for safety, and PK assessments during their participation in this study as noted in [Table 4](#) below:

Table 4. Approximate Blood Volume Collection

Test	Volume per Collection, mL	Number of Collections	Total Volume, mL
Clinical Chemistry	5	5	25
Troponin I	5	4	20
Clinical Hematology	5	5	25
Serum pregnancy test (females only)	5	1	5
HIV/Hepatitis B, C Panel	15	1	15
Serum FSH (females only)	5	1	5
AMG 986 PK plasma concentration	5	12	60
TOTAL (All Groups)			155

7.4 Sample Storage and Destruction

Any blood sample collected according to the Schedule of Assessments can be analyzed for any of the tests outlined in the protocol and for any tests necessary to minimize risks to study subjects. This includes testing to ensure analytical methods produce reliable and valid data throughout the course of the study. This can also include, but is not limited to, investigation of unexpected results, incurred sample reanalysis, and analyses for method transfer and comparability.

All samples and associated results will be coded prior to being shipped from the site for analysis or storage. Samples will be tracked using a unique identifier that is assigned to the samples for the study. Results are stored in a secure database to ensure confidentiality.

If informed consent is provided by the subject, Amgen can do additional testing on remaining samples (ie, residual and back-up) to investigate and better understand the aspects of AMG 986 (mechanism of action/target, metabolites) and to be applied in assay development. Results from this analysis are to be documented and maintained, but are not necessarily reported as part of this study. Samples can be retained for up to 20 years.

Since the evaluations are not expected to benefit the subject directly or to alter the treatment course, the results of these exploratory studies are not placed in the subject's medical record and are not to be made available to the subject, members of the family, the personal physician, or other third parties, except as specified in the informed consent.

The subject retains the right to request that the sample material be destroyed by contacting the investigator. Following the request from the subject, the Investigator is to provide the sponsor with the required study and subject number so that any remaining samples and any other components from the cells can be located and destroyed. Samples will be destroyed once all protocol-defined procedures are completed. However, information collected from samples prior to the request for destruction, will be retained by Amgen.

The sponsor is the exclusive owner of any data, discoveries, or derivative materials from the sample materials and is responsible for the destruction of the sample(s) at the request of the subject through the investigator, at the end of the storage period, or as appropriate (eg, the scientific rationale for experimentation with a certain sample type no longer justifies keeping the sample). If a commercial product is developed from this research project, the sponsor owns the commercial product. The subject has no commercial rights to such product and has no commercial rights to the data, information, discoveries, or derivative materials gained or produced from the sample. See [Section 11.3](#) for subject confidentiality.

8. WITHDRAWAL FROM TREATMENT, PROCEDURES, AND STUDY

8.1 Subjects' Decision to Withdraw

Subjects have the right to withdraw from the study at any time and for any reason without prejudice to their future medical care by the physician or at the institution.

Subjects (or a legally acceptable representative) can decline to continue receiving AMG 986 and/or other protocol-required therapies or procedures at any time during the study but continue participation in the study. If this occurs, the investigator is to discuss with the subject the appropriate processes for discontinuation from AMG 986, device or other protocol-required therapies and must discuss with the subject the options for continuation of the Schedule of Assessments including different options of follow-up (eg, in person, by phone/mail, through family/friends, in correspondence/communication with other treating physicians, from the review of medical records) and collection of data, including endpoints, adverse events. Subjects who have discontinued AMG 986 and/or protocol required therapies or procedures should not be automatically removed from the study. Whenever safe and feasible it is imperative that subjects remain on-study to ensure safety surveillance and/or collection of outcome data. The investigator must document the level of follow-up that is agreed to by the subject.

Withdrawal of consent for a study means that the subject does not wish to receive further protocol-required therapies or procedures, and the subject does not wish to or is unable to continue further study participation. Subject data up to withdrawal of consent will be included in the analysis of the study, and where permitted, publically available data can be included after withdrawal of consent. The investigator is to discuss with the subject appropriate procedures for withdrawal from the study.

8.2 Investigator or Sponsor Decision to Withdraw or Terminate Subjects' Participation Prior to Study Completion

The investigator and/or sponsor can decide to withdraw a subject(s) from investigational product, medical device(s), and/or other protocol required therapies, protocol procedures, or the study as a whole at any time prior to study completion.

Subjects may be eligible for continued treatment with Amgen investigational product(s) and/or other protocol required therapies by a separate protocol or as provided for by the local country's regulatory mechanism, based on parameters consistent with [Section 12.1](#).

8.3 Reasons for Removal From Treatment or Study

8.3.1 Reasons for Removal From Treatment

Reasons for removal from protocol-required investigational product(s) or procedural assessments include any of the following:

- subject request
- safety concern (eg, due to an adverse event, ineligibility determined, protocol deviation, non-compliance, requirement for alternative therapy, pregnancy)
- death
- lost to follow-up
- decision by sponsor (other than subject request, safety concern, lost to follow-up)
- disease flare

8.3.2 Reasons for Removal From Study

Reasons for removal of a subject from the study are:

- decision by sponsor
- withdrawal of consent from study
- death
- lost to follow-up

Approved

9. SAFETY DATA COLLECTION, RECORDING, AND REPORTING

9.1 Definition of Safety Events

9.1.1 Disease Related Events

Not applicable

9.1.2 Adverse Events

An adverse event is defined as any untoward medical occurrence in a clinical trial subject. The event does not necessarily have a causal relationship with study treatment. The investigator is responsible for ensuring that any adverse events observed by the investigator or reported by the subject are recorded in the subject's medical record.

The definition of adverse events includes worsening of a pre-existing medical condition. Worsening indicates that the pre-existing medical condition or underlying disease (eg, diabetes, migraine headaches, gout) has increased in severity, frequency, and/or duration more than would be expected and/or has an association with a significantly worse outcome than expected. A pre-existing condition that has not worsened more than anticipated (ie, more than usual fluctuation of disease) during the study, or involves an intervention such as elective cosmetic surgery or a medical procedure while on study, is not considered an adverse event.

If the severity of an adverse event changes from the date of onset to the date of resolution, record as a single event with the worst severity on the Event CRF.

The investigator's clinical judgment is used to determine whether a subject is to be removed from treatment due to an adverse event. In the event a subject, or subject's legally acceptable representative requests to withdraw from protocol-required therapies or the study due to an adverse event, refer to [Section 8.1](#) for additional instructions on the procedures recommended for safe withdrawal from protocol-required therapies or the study.

9.1.3 Serious Adverse Events

A serious adverse event is defined as an adverse event that meets at least 1 of the following serious criteria:

- fatal
- life threatening (places the subject at immediate risk of death)
- requires in patient hospitalization or prolongation of existing hospitalization
- results in persistent or significant disability/incapacity
- congenital anomaly/birth defect
- other medically important serious event

An adverse event would meet the criterion of “requires hospitalization”, if the event necessitated an admission to a health care facility (eg, overnight stay).

If an investigator considers an event to be clinically important, but it does not meet any of the serious criteria, the event could be classified as a serious adverse event under the criterion of “other medically important serious event”. Examples of such events could include allergic bronchospasm, convulsions, blood dyscrasias, drug induced liver injury (DILI) (see [Appendix A](#) for DILI reporting criteria), or events that necessitate an emergency room visit, outpatient surgery, or urgent intervention.

9.2 Safety Event Reporting Procedures

9.2.1 Adverse Events

9.2.1.1 Reporting Procedures for Adverse Events That do not Meet Serious Criteria

The investigator is responsible for ensuring that all adverse events observed by the investigator or reported by the subject that occur after dose of investigational product through the Safety Follow-Up Visit/End of Study Visit are reported using the Event CRF.

The investigator must assign the following adverse event attributes:

- Adverse event diagnosis or syndrome(s), if known (if not known, signs or symptoms),
- Dates of onset and resolution (if resolved),
- Severity [and/or toxicity per protocol],
- Assessment of relatedness to investigational product (AMG 986), and/or any study-mandated activity/procedure(s), and
- Action taken

The adverse event grading scale used will be the Common Terminology Criteria for Adverse Events (CTCAE) version 4. The grading scale used in this study is described in [Appendix A](#).

The investigator must assess whether the adverse event is possibly related to the investigational product (AMG 986). This relationship is indicated by a “yes” or “no” response to the question: Is there a reasonable possibility that the event may have been caused by the investigational product? Relatedness means that there are facts or reasons to support a relationship between investigational product and the event.

The investigator must assess whether the adverse event is possibly related to any study mandated activity (eg, administration of investigational product, protocol-required therapies, use of medical device(s) and/or procedure (including any screening procedure(s))). This relationship is indicated by a “yes” or “no” response to the question:

“Is there a reasonable possibility that the event may have been caused by a study activity (eg, administration of investigational product, protocol-required therapies, use of medical device(s)), and/or procedure”?

The investigator is responsible for reviewing laboratory test results and determining whether an abnormal value in an individual study subject represents a clinically significant change from the subject’s baseline values. In general, abnormal laboratory findings without clinical significance (based on the Investigator’s judgment) are not to be recorded as adverse events. However, laboratory value changes that require treatment or adjustment in current therapy are considered adverse events. Where applicable, clinical sequelae (not the laboratory abnormality) are to be recorded as the adverse event.

The investigator is expected to follow reported adverse events until stabilization or reversibility.

9.2.1.2 Reporting Procedures for Serious Adverse Events

The investigator is responsible for ensuring that all serious adverse events observed by the investigator or reported by the subject that occur after signing of the informed consent through 30 days after the dose of Investigational product (AMG 986) or the Safety Follow-Up Visit/End of Study Visit, whichever is later are recorded in the subject’s medical record and are submitted to Amgen. All serious adverse events must be submitted to Amgen within 24 hours following the investigator’s knowledge of the event via the Event CRF.

If the electronic data capture (EDC) system is unavailable to the site staff to report the serious adverse event, the information is to be reported to Amgen via an electronic Serious Adverse Event (eSAE) Contingency Report Form within 24 hours of the investigator’s knowledge of the event. See [Appendix B](#) for a sample of the Serious Adverse Event Worksheet/electronic Serious Adverse Event Contingency Report Form. For EDC studies where the first notification of a Serious Adverse Event is reported to Amgen via the eSerious Adverse Event Contingency Report Form, the data must be entered into the EDC system when the system is again available.

The investigator must assess whether the serious adverse event is possibly related to the investigational product (AMG 986). This relationship is indicated by a “yes” or “no” response to the question: Is there a reasonable possibility that the event may have been

Approved

caused by the investigational product? Relatedness means that there are facts or reasons to support a relationship between investigational product and the event.

The investigator must assess whether the serious adverse event is possibly related to any study-mandated activity or procedure. This relationship is indicated by a “yes” or “no” response to the question: “Is there a reasonable possibility that the event may have been caused by a study activity/procedure”?

The investigator is expected to follow reported serious adverse events until stabilization or reversibility.

New information relating to a previously reported serious adverse event must be submitted to Amgen. All new information for serious adverse events must be sent to Amgen within 24 hours following knowledge of the new information. If specifically requested, the investigator may need to provide additional follow-up information, such as discharge summaries, medical records, or extracts from the medical records.

Information provided about the serious adverse event must be consistent with that recorded on the Event CRF.

If a subject is permanently withdrawn from protocol-required therapies because of a serious adverse event, this information must be submitted to Amgen.

Amgen will report serious adverse events and/or suspected unexpected serious adverse reactions as required to regulatory authorities, investigators/institutions, and IRBs/IECs in compliance with all reporting requirements according to local regulations and good clinical practice.

The investigator is to notify the appropriate IRB/IEC of serious adverse events occurring at the site and other adverse event reports received from Amgen, in accordance with local regulatory requirements and procedures.

9.2.1.3 Reporting Serious Adverse Events After the Protocol-required Reporting Period

There is no requirement to monitor study subjects for serious adverse events following the protocol-required reporting period or after end of study. However, these serious adverse events can be reported to Amgen. In some countries (eg, European Union [EU] member states), investigators are required to report serious adverse events that they become aware of after end of study. If serious adverse events are reported, the investigator is to report them to Amgen within 24 hours following the investigator’s knowledge of the event.

Serious adverse events reported outside of the protocol-required reporting period will be captured within the safety database as clinical trial cases for the purposes of expedited reporting.

9.3 Pregnancy and Lactation Reporting

If a female subject becomes pregnant, or a male subject fathers a child, while the subject is taking Amgen Investigational Product (AMG 986) report the pregnancy to Amgen Global Patient Safety as specified below.

In addition to reporting any pregnancies occurring during the study, investigators should report pregnancies that occur through 11 weeks after the dose of Amgen Investigational Product (AMG 986).

The pregnancy should be reported to Amgen Global Patient Safety within 24 hours of the investigator's knowledge of the pregnancy. Report a pregnancy on the Pregnancy Notification Worksheet ([Appendix C](#)). Amgen Global Patient Safety will follow-up with the investigator regarding additional information that may be requested.

If a female subject becomes pregnant during the study, the investigator should attempt to obtain information regarding the birth outcome and health of the infant.

If the outcome of the pregnancy meets a criterion for immediate classification as a Serious Adverse Event (eg, female subject experiences a spontaneous abortion, stillbirth, or neonatal death or there is a fetal or neonatal congenital anomaly) the investigator will report the event as a Serious Adverse Event.

If a female breastfeeds while taking protocol-required therapies report the lactation case to Amgen as specified below.

In addition to reporting a lactation case during the study, investigators should report lactation cases that occur through 11 weeks after the dose of protocol-required therapies (AMG 986).

Any lactation case should be reported to Amgen Global Patient Safety within 24 hours of the Investigator's knowledge of event. Report a lactation case on the Lactation Notification Worksheet ([Appendix C](#)). Amgen Global Patient Safety will follow-up with the investigator regarding additional information that may be requested.

If a male subject's female partner becomes pregnant, the investigator should discuss obtaining information regarding the birth outcome and health of the infant from the pregnant partner.

Men whose partners become pregnant while the subject is on study through 11 weeks after receiving the dose of study drug must practice sexual abstinence or use a condom for 11 weeks after receiving the dose of study drug, and will be followed for safety until the end-of-study visit.

10. STATISTICAL CONSIDERATIONS

10.1 Study Endpoints, Analysis Sets, and Covariates

10.1.1 Study Endpoints

10.1.1.1 Primary Endpoints

- AMG 986 PK parameters including area under the plasma concentration time curve from time 0 to the time of the last quantifiable sample (AUC_{0-t}) and maximum observed plasma concentration after dosing (C_{max}). Additional AMG 986 PK parameters may include but not limited to terminal phase half-life ($t_{1/2}$); time of maximum AMG 986 plasma concentration (t_{max}); and AUC from time 0 to infinity (AUC_{inf}).

10.1.1.2 Secondary Endpoint

- Subject incidence of adverse events and clinically significant changes in vital signs, physical examinations, clinical laboratory tests, and ECGs

10.1.1.3 Exploratory Endpoints

- Plasma protein binding of AMG 986
- AMG 986 metabolite concentrations in plasma

10.1.2 Analysis Sets

For all analyses, subjects will be analyzed according to the group they were assigned.

10.1.2.1 Safety Analysis Set

The safety analysis set will consist of all study subjects who receive at least one dose of AMG 986. Subjects withdrawing prior to AMG 986 administration due to adverse events related to study procedure will not be included in the safety analysis set but those adverse events will be included in the adverse events listing for all enrolled subjects.

10.1.2.2 Pharmacokinetic (PK) Analysis Set

The PK analysis set will consist of all subjects for whom at least one PK parameter or endpoint can be reliably estimated.

10.1.3 Covariates and Subgroups

Baseline values may be used as a covariate in analyses. For any variable, unless otherwise defined, baseline is defined as the last assessment taken prior to the first administration of AMG 986.

Approved

Group 1 will be the group formed with subjects with severely impaired renal function. Group 2, the group formed with subjects with normal renal function, will be considered the control group. An effort will be made to match the subjects in group 2, the normal renal function group to the subjects in group 1, by age range, body weight, gender, and race. The mean age \pm 5 years and mean body weight \pm 10% of the subjects in the severely renal impaired group will be used to help match the subjects in the control group. No subgroup analyses are planned.

10.1.4 Handling of Missing and Incomplete Data

Incomplete data in the Primary Endpoints will be excluded from analysis. The number and frequency of missing values will be reported in the final study report.

Imputation for missing or incomplete dates will be performed, if required. If imputed dates are used, they will be identified as such in the final study report.

PK concentrations below the lower limit of quantification will be set to zero.

10.2 Sample Size Considerations

This is a Phase 1 study and no formal statistical hypothesis testing will be performed. The study is designed to characterize AMG 986 PK and safety plus tolerability, following a single oral administration of a 200-mg dose by descriptive summaries based on the observed data. The sample size of this study is based on practical considerations and is consistent with the number of subjects enrolled in similar studies. Approximately 12 subjects (6 subjects with severe RI and 6 subjects with normal renal function) will be enrolled for the study. Assuming 20% for the intra-subject standard deviation for AMG986 log-transformed PK parameters (AUC_{0-t} and C_{max}) and assuming that it is the same in the 2 groups, the current sample size of 6 would provide a Confidence Interval for the Geometric Mean Ratio of the parameters of (0.81, 1.23). For safety considerations, with a total of 12 subjects receiving AMG 986, there is a 46% chance of detecting an adverse event with a true incidence of 5% and a 72% chance of detecting a more common adverse event with a true incidence rate of 10%.

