5.1 Treatment Assignment

This is a phase 1, open-label, non-randomized study conducted in subjects with severely impaired renal function as determined by the modification of diet in renal disease (MDRD) equation for estimated glomerular filtration rate (eGFR). Subjects who meet eligibility requirements ([Section 4](#)) will be assigned into one of 2 treatment groups: severe RI (eGFR 15 to 29 mL/min/1.73 m²) or normal renal function (eGFR ≥ 90 mL/min/1.73 m² or above).

Subjects with severely impaired renal function (eGFR 15 to 29 ml/min/1.73 m²) will be assigned to group 1. Subjects with normal renal function will be assigned to the control group 2. Enrollment of subjects in the control group will be initiated after all subjects in the RI group have been enrolled.

An attempt will be made to match the control group of healthy males and females with normal renal function (group 2) to the group of subjects with severely impaired renal function (group 1) by age range, body weight range, gender (proportion of male and female subjects), and race. The mean age ± 5 years and mean body weight ± 10% of the subjects in the severely renal impaired group will be used to help match the subjects

Approved

in the control group. The priority for matching subject characteristics of the two groups will be: age range, body weight range, gender, then race. After review of the characteristics of the subjects enrolled in the RI group, Amgen will decide on the acceptability of eligible subjects in the control group to match the RI group, and be enrolled in the study.

All subjects in each group will receive a single oral dose of 200 mg AMG 986 on day 1. Subjects will be assigned an identification number in the order in which they were qualified.

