10.4.2 Primary Endpoints

10.4.2.1 Pharmacokinetic Analysis

The PK parameters for each subject will be estimated using non-compartmental methods. All plasma concentrations below the limit of quantification of the assay will be considered as zero for all analyses unless explicitly noted otherwise.

Summary statistics will be provided for each renal function group for AMG 986 PK parameters. These parameters will include AUC_{0-inf} , AUC_{0-t} , C_{max} , t_{max} , $t_{1/2}$ as appropriate. Binding of AMG 986 to plasma proteins will be determined to calculate select unbound PK parameters, if appropriate, and summary statistics will be provided. Graphs of AMG 986 plasma concentration-time profiles for individual subjects and for means for each function group may be provided. The mean difference for the 2 groups will be back transformed to produce the geometric mean ratio. Lower and upper limits of the 90% confidence interval for these ratios of the PK parameters will also be reported.

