3.2 Sample Size

This is a Phase 1 study and no formal statistical hypothesis testing will be performed. The study is designed to characterize AMG 986 PK and safety plus tolerability, following a single oral administration of a 200-mg dose by descriptive summaries based on the observed data. The sample size of this study is based on practical considerations and is consistent with the number of subjects enrolled in similar studies. Approximately 12 subjects (6 subjects with severe RI and 6 subjects with normal renal function) will be enrolled for the study. Assuming 20% for the intra-subject standard deviation for AMG 986 log-transformed PK parameters (AUC_{0-t} and C_{max}) and assuming that it is the same in the 2 groups, the current sample size of 6 would provide a Confidence Interval for the Geometric Mean Ratio of the parameters of (0.81, 1.23). For safety

considerations, with a total of 12 subjects receiving AMG 986, there is a 46% chance of detecting an adverse event with a true incidence of 5% and a 72% chance of detecting a more common adverse event with a true incidence rate of 10%.

4. Covariates and Subgroups

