9.7 Other Analyses

9.7.1 Analyses of Pharmacokinetic Endpoints

The PK parameters for each subject will be estimated using non-compartmental methods and will be performed by the Clinical Pharmacology, Modeling & Simulation group (CPMS). Actual dosing and sampling times will be used for calculation of PK

parameters. All plasma concentrations below the limit of quantification of the assay will be considered as zero for all analyses unless explicitly noted otherwise.

Summary statistics will be provided for each renal function group for AMG 986 PK parameters. These parameters will include AUC_{0-inf} , AUC_{0-t} , C_{max} , t_{max} , $t_{1/2}$ as appropriate. Graphs of AMG 986 plasma concentration-time profiles for individual subjects and for means for each function group may be provided.

Geometric means and 90% CI for the ratio of the geometric means (group 1/ group 2) will be estimated using ANOVA model. The model will use the log-transformed PK parameters as the dependent variable (or response) and renal function group as independent variable. The mean difference for the 2 groups will be back transformed to produce the geometric mean ratio. Lower and upper limits of the 90% confidence interval for these ratios of the PK parameters will also be reported.

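### The planned interval of (0.81, 1.23) for the geometric mean ratio uses a 20% intra-subject SD in a parallel, single-dose design; the protocol's own 200 mg data give about (0.71, 1.41)

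*Protocol*

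**What the plan says.** Protocol 10.2 sets the size on practical grounds: "Approximately 12 subjects (6 subjects with severe RI and 6 subjects with normal renal function) will be enrolled for the study". It then states the precision this gives for AUC0-t and Cmax: "Assuming 20% for the intra-subject standard deviation for AMG986 log-transformed PK parameters" and "assuming that it is the same in the 2 groups", leading to an interval for the GMR of (0.81, 1.23). SAP 3.2 repeats the assumption ("Assuming 20% for the intra-subject standard deviation for AMG 986 log-transformed PK parameters") and the interval, as does the Statistical Considerations part of the synopsis. Protocol 10.2 and SAP 3.2 do not give the confidence level. No source is given for the 20%.

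The design is described in Protocol 5.1: "This is a phase 1, open-label, non-randomized study conducted in subjects with severely impaired renal function", and "All subjects in each group will receive a single oral dose of 200 mg AMG 986 on day 1". The analysis is in SAP 9.7.1: "Geometric means and 90% CI for the ratio of the geometric means (group 1/ group 2) will be estimated using ANOVA model". Log-transformed parameters are the response and renal function group is the only factor. Protocol 10.4.2.1 gives the reporting level: "Lower and upper limits of the 90% confidence interval for these ratios of the PK parameters will also be reported".

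Protocol 2.2.2, Table 1, gives preliminary first-in-human results after single oral doses in healthy subjects. At 200 mg the CV is 34% for Cmax and 33% for AUCinf.

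**The concern.** An intra-subject SD describes how one person's exposure varies from one dosing occasion to the next. It drives the precision of a crossover comparison. Here nobody is dosed twice and the two renal function groups contain different people. The error term of the SAP's ANOVA is therefore the total between-subject variance, on 10 degrees of freedom. Intra-subject variance is only one part of that total, so putting an intra-subject SD in its place makes the interval too narrow.

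The protocol also holds between-subject data at the study dose, and they are well above 20%. The documents do not reconcile the two.

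This matters because the sentence is the only quantitative statement of what six per group can deliver for the primary endpoints. The clinical hypothesis (Protocol 2.5, SAP 2.2) is that no PK change large enough to need dose adjustment is expected, and the 90% interval for the GMR is the planned group comparison. A reader of the stated figure would think that, with a GMR of 1, the data would bound an increase at about 23%. On the protocol's own 200 mg figures the bound is about 40%.

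**Working it through.** **Inputs**

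- Subjects per group: 6 and 6 (Protocol 10.2), so 10 degrees of freedom.
- Level: 90%, two-sided (Protocol 10.4.2.1, SAP 9.7.1).
- Assumed log SD: 0.20, equal in both groups (Protocol 10.2).
- Observed CVs by oral dose, 5 / 30 / 100 / 200 mg (Protocol Table 1): Cmax 22, 33, 24, 34%; AUCinf 34, 25, 5, 33%. The data come from 24 oral-dose subjects in 4 cohorts (Protocol 2.2.2), or 24/4 = 6 per cohort if equal.

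**Formula**

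For a GMR of 1, the limits are exp(± t(0.95, 10) × SD × sqrt(1/6 + 1/6)), with t = 1.8125 and sqrt(1/3) = 0.5774. A CV is converted by SD(log) = sqrt(ln(1 + CV²)).

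**Step 1: reproduce the plan's figure**

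Half-width = 1.8125 × 0.20 × 0.5774 = 0.2093, giving (0.811, 1.233). This matches (0.81, 1.23). Reading 20% as a CV gives (0.813, 1.230), which also matches. A normal quantile gives (0.827, 1.209) and a 95% t-interval gives (0.773, 1.293); neither matches. So the plan used the two-sample 90% t-interval, with 0.20 in the place of the between-subject SD. The arithmetic is right for that input.

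**Step 2: use the protocol's between-subject variability**

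| Input | log SD | Half-width | 90% limits at GMR = 1 | Width relative to plan (log scale) |
|---|---|---|---|---|
| Plan | 0.200 | 0.209 | (0.81, 1.23) | 1.00 |
| Cmax, 200 mg, CV 34% | 0.331 | 0.346 | (0.71, 1.41) | 1.65 |
| AUCinf, 200 mg, CV 33% | 0.322 | 0.336 | (0.71, 1.40) | 1.61 |
| Cmax, four doses pooled, CV about 29% | 0.281 | 0.294 | (0.75, 1.34) | 1.41 |
| AUCinf, four doses pooled, CV about 27% | 0.263 | 0.275 | (0.76, 1.32) | 1.31 |
| CV 40% (assumption: impaired subjects vary more) | 0.385 | 0.403 | (0.67, 1.50) | 1.93 |

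Pooled SDs are the square root of the mean of the four log variances. For Cmax: sqrt((0.0473 + 0.1034 + 0.0560 + 0.1094)/4) = 0.281. For AUCinf: sqrt((0.1094 + 0.0606 + 0.0025 + 0.1034)/4) = 0.263.

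**Step 3: chance of an interval as narrow as stated**

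This is P(chi-square on 10 df ≤ 10 × (0.20/SD)²). It is 4% at CV 34% and 5% at CV 33%. At the pooled SDs it is 11% (Cmax) and 17% (AUC).

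**Step 4: what the stated precision would need**

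An upper limit near 1.23 would take about 14 subjects per group at CV 33%, giving (0.81, 1.23), or 15 at CV 34%, also giving (0.81, 1.23).

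**The case against.** The strongest reply is that nothing in the trial depends on this figure. No formal test is planned, the sample size was not derived from the 20%, and no margin or decision rule uses (0.81, 1.23). The reported interval will use the variance actually observed, so no estimate is biased. All of this is true. It limits the fault to the stated precision, but it does not make that statement correct.

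A second reply is that intra-subject may be only a wrong label. If so, 20% is an unsourced between-subject SD well below the protocol's own 200 mg values, and precision is still overstated. Matching does not rescue it either: it works on group mean age and weight, and the model has no pair term.

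A third reply is that the 200 mg CVs come from one small, preliminary cohort. With six subjects and approximately log-normal data, 95% limits for the log SD are 0.206 to 0.811 (Cmax) and 0.201 to 0.789 (AUC). Cmax CVs at 5 and 100 mg were 22% and 24%; a CV of 22% gives (0.80, 1.26), close to the plan. The limits of about 0.71 and 1.41 should therefore not be read as precise. But pooling all four doses, including the 5% AUC value at 100 mg, still gives wider intervals than stated. With six per cohort, pooled variability this high would arise about 0.6% (Cmax) or 2% (AUC) of the time if the true SD were 0.20.

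Last, Table 1 gives AUCinf, not AUC0-t, and covers healthy subjects only. Sampling runs to 120 hours and mean half-lives were 13.2 to 18.0 hours. That is at least 120/18 = 6.7 half-lives, so the two AUCs should nearly coincide unless renal impairment greatly prolongs the half-life. Cmax does not have this difficulty. The documents give no variability for severe renal impairment, and that gap remains.

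**Conclusion.** The concern holds. The formula is right, but the variance component named in the plan is the wrong one for this design, and its value disagrees with the protocol's own data at the study dose. With the 200 mg CVs, six per group give 90% limits of about (0.71, 1.41) for Cmax and (0.71, 1.40) for AUC, against the stated (0.81, 1.23). On the pooled oral data the overstatement is smaller but still present: (0.75, 1.34) and (0.76, 1.32).

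This rests on log-normal parameters, equal variance in the two groups, CVs in Table 1 that reflect variation between subjects given one dose each, and healthy-subject variability carrying over to severe impairment. Table 1 does not say whether its CVs are arithmetic or geometric. Using them directly as log SDs changes the limits little: (0.70, 1.43) for Cmax and (0.71, 1.41) for AUC.

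**What to change.** Replace the precision sentence in Protocol 10.2, the synopsis and SAP 3.2 with text such as:

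> *Assuming a between-subject CV of 34% for Cmax and 33% for AUC (preliminary data, healthy subjects, 200 mg oral cohort, Study 20150183), equal in the two groups, 6 subjects per group give a 90% CI of about (0.71, 1.41) for Cmax and (0.71, 1.40) for AUC when the GMR is 1. With CVs pooled over the four oral doses (about 29% and 27%) the intervals are (0.75, 1.34) and (0.76, 1.32); with a CV of 40% the interval is (0.67, 1.50).*

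Add that the AUC figure is taken from AUCinf and that variability in severe renal impairment is not known. If the sponsor has a source for 20% as a between-subject SD, cite it and explain why it is preferred to Table 1.

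Keep 12 subjects on the practical grounds already given. The cost is wording in three places and a less favourable stated precision. No subjects are added and the analysis does not change.
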